1. PROTOCOL SYNOPSIS FOR STUDY 201840

Rationale

Albiglutide is a long-acting glucagon-like peptide-1 (GLP-1) receptor (GLP-1R) agonist (Tmax 3-5 days) that has been developed as a once weekly subcutaneous injection treatment of type 2 diabetes mellitus (T2DM) and approved by the US Food and Drug Administration (FDA), the European Medicines Agency (EMA) and other regulatory agencies. In clinical trials, nausea is a common side effect of the currently marketed GLP-1R agonists. It is not clear whether nausea associated with GLP-1R agonists is caused by stimulation of GLP-1R in the gastrointestinal system, by activation of the nausea centers at the central nervous system (CNS) via vagal afferent fibers, by direct activation of GLP-1R in the brain following blood-brain barrier penetration, or by combination of peripheral and central GLP-1R activation as the most likely mechanisms. Although the various GLP-1R agonists share the same receptor and basic mechanisms of action, differences in pharmacokinetic and pharmacodynamic characteristics may translate into differential clinical effects and tolerability profiles, with differences in the incidence of nausea in clinical trials. The dose- and time-dependent efficacy and safety effects of albiglutide were evaluated in a phase 2b dose ranging, open-label, active reference (exenatide) study. The study included two albiglutide 50 mg dosing regimens (biweekly and monthly). Exenatide 5 µg bid was up-titrated to 10 µg after 4 weeks consistent with the label to maximize tolerability. The change in HbA1c after 16 weeks was -0.79% and -0.55% for the 50 mg albiglutide biweekly and monthly regimens, respectively, and -0.54% for exenatide. The peak weekly incidence of nausea and/or vomiting for 50 mg albiglutide (without up-titration) was 25.7%. Exenatide 5 µg up-titrated to 10 µg resulted in a peak weekly incidence of nausea or vomiting of 29%. The peak weekly incidence of nausea alone was 25.7% for the 50 mg albiglutide regimens (without up-titration) and 22.6% for exenatide (up-titrated) after 4 weeks [GlaxoSmithKline Document Number [ZC2007/00001/00](#)].

To gain insight into the physiologic pathways leading to nausea associated with GLP-1R agonists, this study will explore the regional differences in brain activity and connectivity in healthy volunteers receiving single doses of albiglutide or exenatide, a short acting GLP-1R agonist that has been shown to cross the blood brain barrier in mice after peripheral administration [[Kastin, 2003](#)]. There are no human data of blood brain barrier penetration with albiglutide although limited transfer has been suggested in a murine model [GlaxoSmithKline Document Number [2015N232567_00](#)]. For both drugs, brain activity will be assessed at the expected time of Cmax using functional magnetic resonance imaging (fMRI) to assess changes in blood oxygen level dependent (BOLD) signal in the resting-state BOLD, arterial spin labeling (ASL), and magnetic resonance spectroscopy (MRS). fMRI will be assessed without drug while nausea is induced observing the rotation of vertical stripes in a rotating drum to create the illusion of self motion (vection).

Objective(s)/Endpoint(s)

Objectives	Endpoints
Primary	

 To explore the effect of single dose 50 mg albiglutide compared to single dose 10 µg exenatide on regional brain activity and connectivity associated with nausea in healthy volunteers 	
 Resting-state BOLD signal (fMRI) Regional cerebral blood flow (rCBF) (fMRI-ASL) Glutamate concentration in nausea-associated brain regions (MRS) GABA concentration in nausea-associated brain regions (MRS)
Secondary	

 To evaluate autonomic effects of single dose 50 mg albiglutide compared to single dose 10 µg exenatide To assess safety and tolerability of single dose 50 mg albiglutide and single dose 10 µg exenatide 	
 Heart rate, heart rate variability, respiratory rate, ECG intervals, blood pressure, skin conductance level Vital signs, clinical laboratory tests, adverse events, Nausea ratings scale, GI-VAS and MSAQ
Exploratory	

 To evaluate gastric myoelectrical activity (GMA) of single dose 50 mg albiglutide compared to single dose 10 µg exenatide 	
 GMA: description of frequency region(s) (Bradygastria, Normal, Tachygastria)

Overall Design

This is a phase IV, 2-part, 2-period crossover, single dose, randomized, single blind (blinded to both the subject and the imaging evaluators analysing the MRI data), placebo- and active-controlled study in adult healthy volunteers susceptible to motion sickness. The study is designed to evaluate if albiglutide and exenatide modulate nausea-related brain activity and connectivity as assessed by MRI. Placebo is used to enable albiglutide and exenatide to be dosed at different times relative to MRI due to differences in Tmax, while preserving single-blind.

The two parts of the study, Part A and Part B are the same in design, both consisting of a screening stage, a dosing/assessment stage, and a follow-up visit. Part A will test the acquisition parameters and scanning paradigms for Part B. Part A will initially randomize 4 subjects. Based on data review from the initial 4 subjects, an additional 4 subjects may be randomized for Part A. Reasons to enroll a second cohort include the need to modify acquisition parameters and scanning paradigms. If the modifications are substantial, a second cohort of 4 subjects will be added to Part A before progressing to Part B. Part B will randomize 20 subjects. Data from the Part A will inform progression, methods, and analysis plan for Part B.

After screening, eligible subjects will be randomized to one of the four crossover dosing/imaging sequences, shown in study design figure below, which include two dosing/imaging sessions and one washout period between them. Subjects will return for a follow-up visit post last dosing.

Session 1 and Session 2 each consist of 2 or 3 single-day out-patient visits according to the randomization schedule. There will be a 6-9 week washout period between Session 1 and Session 2.

- Day 1 (Session 1 or 2 per randomization) for an off-therapy MRI scan, consisting of resting-state fMRI, a nauseogenic task fMRI, ASL and MRS, and nausea associated assessments,
- Day 5 for a single dose of 50 mg albiglutide or albiglutide placebo, and
- Day 8 for a single dose of 10 µg exenatide or saline injection (exenatide placebo) followed by a post-dose MRI scan consisting of resting-state fMRI, ASL and MRS, and nausea associated assessments.

Note: Off-therapy MRI and post-dose MRI both include MRS, ASL, and resting state BOLD. In addition, the Off-therapy MRI will include a visual nauseogenic task fMRI (See Time and Events tables for full list of assessments during scan). *Number of subjects can be increased in Part A based on imaging evaluators' judgment in consultation with the Investigator and Sponsor after data review from 4 subjects

Treatment Arms and Duration

In either Part A or Part B, the total duration of a subject's participation is approximately 15-19 weeks, assuming up to 4 weeks for screening, 8 days each for Session 1 and Session 2, 6 to 9 weeks for washout, and a 4 weeks post last treatment follow-up.

Subjects will be randomized to one of the following treatment sequences:

Sequence	Session 1 ^a			Session 2 ^a		
1	Off-therapy MRI	50 mg albiglutide	placebo ^c (post-dose MRI)		placebo ^b	10 µg exenatide (post-dose MRI)
2		50 mg albiglutide	placebo ^c (post-dose MRI)	Off-therapy MRI	placebo ^b	10 µg exenatide (post-dose MRI)
3	Off-therapy MRI	placebo ^b	10 µg exenatide (post-dose MRI)		50 mg albiglutide	placebo ^c (post-dose MRI)
4		placebo ^b	10 µg exenatide (post-dose fMRI)	Off-therapy MRI	50 mg albiglutide	placebo ^c (post-dose MRI)

- a. All administration will be given at fixed dose once daily by subcutaneous injection.
- b. Placebo pen for albiglutide

- c. Saline injection will be given as placebo for exenatide

All doses will be given in the morning. Overnight fasting is always required prior to MRI sessions (see details in Section 6.10.1). It is recommended that the MRI scan be scheduled for early in the morning at the same time of day for each subject for all MRI scanning sessions.

Type and Number of Subjects

Part A will initially randomize 4 subjects. Based on data review from the initial 4 subjects, an additional 4 subjects may be randomized for Part A. Part B will randomize 20 subjects.

Analysis

Data from Parts A and B will be pooled, as appropriate, for final analysis. For comparisons between albiglutide and exenatide, analysis of variance (ANOVA) will be used to analyze quantifiable endpoints with treatment and period as fixed effects, and subject as random effect. Pearson's and Spearman's correlation coefficients will be used to review relationships between selected quantifiable end points. A minimum of four subjects will be enrolled and analyzed in Part A (Cohort 1). Based on the results, a decision to enroll 4 additional subjects could be taken (Cohort 2). The criteria for this decision will be based on clinical (e.g., safety) and technical judgment after review of the neuroimaging data. Changes in brain activity associated with exenatide or albiglutide in imaging modalities tested will inform progression, methods, and analysis plan to Part B. For each subject adverse events will be reviewed by the Medical Monitor in both Parts A and B prior to the next subject being studied. Data analysis for Part A and Part B will be exploratory. The analysis plan for Part B will be finalized based on Part A results.

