6.8. Treatment of Study Treatment Overdose

In the event of an overdose the Investigator should:

1. contact the Medical Monitor immediately
2. closely monitor the subject for adverse events (AEs)/serious adverse events (SAEs) and laboratory abnormalities until albiglutide or exenatide can no longer be detected systemically (at least 25 days for albiglutide or 24 hrs for exenatide).
3. document the quantity of the excess dose as well as the duration of the overdosing in the eCRF.

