7. STUDY ASSESSMENTS AND PROCEDURES

Protocol waivers or exemptions are not allowed with the exception of immediate safety concerns. Therefore, adherence to the study design requirements, including those specified in the Time and Events Table, are essential and required for study conduct.

This section lists the procedures and parameters of each planned study assessment. The exact timing of each assessment is listed in the Time and Events Table Section [7.1](#).

Procedure	Screening	Session 1											Wash out	Session 2						F/U
	Week -4 to -1	Day 1			Day 5±1 ^m	Day 8±1 ^m					Post MRI	6-9 weeks	Day 1	Day 4±1 ^m					Week 13	
		Pre-MRI	MRI	Post MRI		-2 h	-0.5 h	0 h	0.5 h	1 h				0.5 h	1 h	-2 h	-0.5 h	0 h		0.5 h
Randomization	X																			
Dosing albiglutide or placebo ^g					X							X								
Dosing exenatide or placebo ^g							X							X						
MRI ^h		X							X							X				
Autonomic monitoring		X							X							X				
Electrogastrogram		X							X							X				
VAS		X		X				X		X				X		X				
MSAQ ⁱ				X						X							X			
Capillary blood glucose										X							X			
Fasting Plasma Glucose										X							X			
Snack ^j				X						X							X			
AE assessment ^k		<----->			<----->							<----->					X			
Discharge ^l				X						X							X			

- a. Medical history includes alcohol/tobacco/caffeine usage.
- b. Prior-Medications are defined as prescription or over-the counter medications taken within 30 days of Screening. Record concomitant medications and or changes.
- c. WCBP is women of child-bearing potential. Serum pregnancy test at Screening. Urine pregnancy at other specified time points.
- d. If test otherwise performed within 1 month prior to first dose of study treatment, testing at screening is not required.
- e. See Table 2 for list of laboratory parameters. Unscheduled Safety Labs and ECGs can be done at any time if the Investigator considers the assessments appropriate for subject safety.
- f. Mock fMRI is performed on a separate day during the screening period. Scheduling should allow at least 1 week between the Mock fMRI and the next MRI scan.
- g. Albiglutide, exenatide or placebo is administered according to randomization sequence.

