2.3. Study Design

Overview of Study Design and Key Features																																										

Screening Week -4 to -3 Week -2
 
General screening Mock MRI & behavior
		
Session 1 Week 1 Day 1 Day 5 Day 8
			
Wash-out
	
Session 2 Week 9 Day 1 Day 5 Day 8
		
Follow-up Week 13
																																		

Part A n=4 or 8 Part B n=20
 
Randomization
		Off-therapy MRI	albiglutide	*placebo *post-dose MRI	6-9 weeks	placebo	*exenatide *post-dose MRI																																			
			albiglutide	*placebo *post-dose MRI	6-9 weeks	Off-therapy MRI	placebo	*exenatide *post-dose MRI																																		
		Off-therapy MRI	placebo	*exenatide *post-dose MRI	6-9 weeks		albiglutide	*placebo *post-dose MRI																																		
			placebo	*exenatide *post-dose MRI	6-9 weeks	Off-therapy MRI	albiglutide	*placebo *post-dose MRI																																		
Design Features		
 Phase IV, 2-part, 2-period crossover, single dose, randomized, single-blind (blinded to both the subject and the imaging evaluators analysing the MRI data), placebo and active-controlled study in adult healthy volunteers susceptible to motion sickness 																																								

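### Follow-up is set both at 4 weeks after the last treatment and at a fixed Week 13, and the two rules cannot both hold across the permitted 6-9 week washout

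*Protocol*

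**What the plan says.** **Synopsis, Treatment Arms and Duration.** The protocol states that "the total duration of a subject's participation is approximately 15-19 weeks, assuming up to 4 weeks for screening", and then adds "8 days each for Session 1 and Session 2, 6 to 9 weeks for washout, and a 4 weeks post last treatment follow-up".

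**Time and Events tables, protocol Section 7.1.** Both tables head the follow-up column Week 13. The dosing and scan columns carry windows of ±1 day and a footnote tying scan to dose. The follow-up column has neither. Section 7 gives these tables authority: "The exact timing of each assessment is listed in the Time and Events Table Section" 7.1. It also makes adherence to them a requirement of study conduct.

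**SAP.** The design figure in Section 2.3 reads "Session 1 Week 1 Day 1 Day 5 Day 8", then "Session 2 Week 9 Day 1 Day 5 Day 8", then "Follow-up Week 13". Appendix 2 repeats the protocol schedule that has the off-therapy scan in Session 1, again with Week 13.

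**Washout.** The synopsis says "There will be a 6-9 week washout period between Session 1 and Session 2". Section 4.1 also describes it as lying between the dosing scans, and Section 4.4 as lying between injections.

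**What depends on the visit.** Routine adverse-event collection (Section 7.4.1.1), pregnancy reporting (7.4.2) and the contraception requirement (5.1) all run to follow-up. Section 7.4.8 asks for repeat testing of clinically significant laboratory abnormalities found up to 25 days after the last dose.

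**The concern.** The date of the last dose can move by three weeks with the length of the washout. A visit pinned to a study week cannot also stay a fixed distance from that dose. Staff who schedule from the tables and staff who schedule from the synopsis would bring the same subject back on different days.

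Safety and tolerability of each drug is a secondary objective. In Sequences 3 and 4 albiglutide is the second drug, so how long it is observed would depend on which passage was followed and on how long the washout happened to be. The SAP would not reveal this. Section 8.2.4 summarises adverse events by treatment group without a post-dose attribution period, and Appendix 3 counts study days from the first dose only.

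**Working it through.** **1. The plan's own total.** Screening + 8/7 + washout + 8/7 + 4 weeks:
- 4 weeks of screening, 6-week washout: 4 + 2.29 + 6 + 4 = 16.29 weeks.
- 4 weeks of screening, 9-week washout: 4 + 2.29 + 9 + 4 = 19.29 weeks.
- 3 weeks of screening, 6-week washout: 15.29 weeks.

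So the stated 15-19 weeks is reproduced when follow-up moves with the last dose. With the visit fixed at Week 13, the longest total is about 4 + 13 = 17 weeks.

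**2. Week 13 in study days.** The SAP figure starts Week 1 at Session 1, so Week 13 is Days 85-91. For the agreement test I allow Day 92 (28 days after Day 64), which is generous. The two rules agree when last injection + 28 lies in Days 85-92, that is, when the last injection is on Days 57-64.

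**3. Day of the last injection for a washout of w weeks** (nominal visit days). The synopsis and Section 4.1 number the dosing visits Day 5 and Day 8. The Time and Events tables use Day 1 and Day 4 for the session without the off-therapy scan.

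| Reading of washout | Albiglutide (if second) | Last injection | Rules agree for w |
|---|---|---|---|
| Session to session, Day 5/Day 8 in both | 12 + 7w | 15 + 7w | (57−15)/7 = 6.0 to (64−15)/7 = 7.0 |
| Session to session, Time and Events numbering | 8 + 7w | 11 + 7w | 6.57 to 7.57 |
| Scan to scan, Session 1 scan on Day 8 | 5 + 7w | 8 + 7w | 7.0 to 8.0 |
| Scan to scan, Session 1 scan on Day 4 | 1 + 7w | 4 + 7w | 7.57 to 8.57 |

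**4. A 9-week washout with Week 13 taken literally (Days 85-91).**

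| Reading | Last injection | Days to visit | Albiglutide | Days to visit |
|---|---|---|---|---|
| Session to session, Day 5/Day 8 | Day 78 | 7-13 | Day 75 | 10-16 |
| Session to session, Time and Events | Day 74 | 11-17 | Day 71 | 14-20 |
| Scan to scan, Session 1 scan Day 8 | Day 71 | 14-20 | Day 68 | 17-23 |
| Scan to scan, Session 1 scan Day 4 | Day 67 | 18-24 | Day 64 | 21-27 |

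The between-injections wording adds nothing outside these ranges. Counted first injection to first injection, it gives the scan-to-scan rows. Counted from the last injection of Session 1 to the first of Session 2, it gives last injections on Day 74 or Day 70 (4 + 63 + 3), so 11-17 or 15-21 days.

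**5. A 6-week washout, for contrast.** The last injection falls on Day 57, 53, 50 or 46 in the four rows, so Week 13 comes 28-34, 32-38, 35-41 or 39-45 days later. The mismatch therefore runs in both directions.

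**The case against.** The best answer is that Week 13 is a nominal column label. The SAP figure puts Session 2 at Week 9, so Session 2 Day 1 is study Day 57. That is 49 days, or 7 weeks, after Session 1 Day 8. Session 2 Day 8 is then Day 64, and 28 days later is Day 92, the day after Week 13 ends. The labels look like the synopsis rule written out for a mid-range washout. Week 9 cannot be literal for every permitted washout either, and the 19-week total is reachable only if the visit moves with the last dose. This is a plausible account of intent. But neither document says so, and Section 7 calls the tables the exact and required timing.

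Three stronger conclusions are tempting and are not supported:

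- *That the second drug is followed for only one to three weeks.* That needs Week 13 applied literally, a 9-week washout and a session-to-session count. Scan to scan, the visit falls 14-24 days after the last injection and 17-27 days after albiglutide.
- *That safety capture stops while albiglutide is still present.* The protocol's figure of "at least 25 days for albiglutide or 24 hrs for exenatide" belongs to the overdose instructions, and one reading passes 25 days after albiglutide. Nor does all safety follow-up stop at the visit. Section 7.4.1.1 requires notification of related serious events learned of later, Section 7.4.1.3 follows serious events and events of special interest to resolution, and Section 7.4.8 has its own 25-day period. What closes is routine adverse-event collection.
- *That the mismatch is what makes observation of the two drugs unequal.* Even with an exact 4-week follow-up, the first drug is observed through a 6-9 week washout and the second for 4 weeks. The mismatch makes the second interval vary; it does not create the inequality.

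**Conclusion.** The inconsistency stands. The two rules coincide only for washouts of about 6-7.6 weeks (session to session) or 7-8.6 weeks (scan to scan), and a literal Week 13 caps participation at about 17 weeks against a stated 19.

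The shortened follow-up is conditional. If Week 13 is applied as written after a 9-week washout, the visit falls about 7-17 or 14-24 days after the last injection. For albiglutide given second it falls about 10-20 or 17-27 days after that dose. On every reading checked, this is short of the synopsis's 28 days. It is also short of the 25-day laboratory period counted from the last injection, though narrowly at the top: counting Week 13 to Day 92 would bring the last row to exactly 25 days.

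These figures assume nominal visit days, without the ±1-day windows, and Week 1 starting at Session 1 Day 1. The documents do not show which rule was followed in practice, or the actual washouts. SAP Sections 1 and 2.1 say that Part B was cancelled and that four subjects completed Part A. The remaining effect is therefore mainly on how descriptive safety results are reported and read.

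**What to change.** Reconcile the synopsis with both protocol Time and Events tables, the SAP design figure (Section 2.3) and SAP Appendix 2, so that one follow-up timing rule holds for every permitted washout. Which rule is right is for the sponsor; this review does not choose it. The same edit should settle on one definition of the washout, because the three wordings shift the dates. For the completed Part A, the report should state which rule was applied.

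In the SAP:
- List each subject's actual days from last dose to follow-up and, for subjects given albiglutide second, from albiglutide to follow-up.
- In Section 8.2.4, state the post-dose period over which adverse events are attributed to each drug, and summarise them by drug over a period common to both sessions. It can be no longer than the shortest interval actually observed. Events outside it stay in the listings.

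The cost is a wording change in the schedule passages, one or two derived variables and a sentence in Section 8.2.4. No new data are needed for the four subjects.

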2. INTRODUCTION

2.1. Study Rationale

GLP-1R agonists (i.e., exenatide, liraglutide, albiglutide, and dulaglutide) are approved therapies for the treatment of T2DM. These agents mimic the action of endogenous GLP-1 stimulating the release of insulin in a glucose dependent manner and reducing glucagon secretion, effectively lowering fasting plasma glucose and hemoglobin A1c. The most commonly reported adverse events associated with the GLP-1R agonist class are nausea, vomiting and diarrhea. The rate of GI related events vary among the agents [Trujillo, 2015] and the mechanism is not fully understood. It is not clear whether nausea is caused by stimulation of GLP-1R in the gastrointestinal system resulting in delayed gastric emptying, or activation of the nausea centers at the central nervous system (CNS) via vagal afferent fibers, or directly via activation of GLP-1Rs in the brain following blood-brain barrier penetration, or a combination of these mechanisms. GLP-1R agonists share the same receptor and basic mechanisms of action, but there are differences in their pharmacokinetic and pharmacodynamic characteristics that appear to translate into differential tolerability profiles. This difference appears to be most noticeable between long acting and short acting GLP-1 receptor agonists [Østergaard, 2016].

Albiglutide, a long-acting GLP-1R agonist, (T_{max} ~3-5 days), is an analogue of GLP-1 generated through genetic fusion of 2 tandem copies of modified human GLP-1 with 97% amino acid sequence homology to endogenous human GLP-1 fragment 7-36 linked to human albumin (molecular weight: 72,970 Daltons) [TANZEUM (albiglutide) for injection, 2015]. There are no human data of blood brain barrier penetration with albiglutide although limited drug transfer has been suggested in a murine model [GlaxoSmithKline Document Number 2015N232567_00]. Exenatide, a short acting GLP-1R agonist (T_{max} ~2 h), is a synthetic 39 amino acid peptide amide that shares 53% sequence homology with human GLP-1 [Goke, 1993] and with a molecular weight of 4186.6 Daltons [BYETTA for injection, AstraZeneca 2015]. It has been shown to cross the blood brain barrier after peripheral administration in mice [Kastin, 2003]. However, there are conflicting data regarding whether circulating exenatide is able to cross the blood-brain barrier in humans [Schloegl, 2013].

The dose- and time-dependent effects on glycemic control and gastrointestinal (GI) tolerability of albiglutide were evaluated in a Phase IIb dose ranging, open-label study with exenatide as an active reference. The study included two 50 mg albiglutide regimens, biweekly and monthly dosing without up-titration. Exenatide 5 μ g bid was up-titrated to 10 μ g after 4 weeks consistent with the label to maximize tolerability. The change in HbA1c after 16 weeks was -0.79% and -0.55% for the 50 mg albiglutide biweekly and monthly regimens, respectively, and -0.54% for exenatide. The peak weekly incidence of nausea or vomiting for 50 mg albiglutide (biweekly or monthly dosing arms without up-titration) was 25.7%. Exenatide 5 μ g up-titrated to 10 μ g reported a peak weekly incidence of nausea or vomiting of 29%. The peak weekly incidence of nausea alone was 25.7% for the 50 mg albiglutide regimens (without up-titration) and 22.6% for exenatide (up-titrated) after 4 weeks [GlaxoSmithKline Document Number ZC2007/00001/00].

There continues to be an interest in the mechanism underlying the GI side effects with GLP-1R agonists [Smits, 2015]. To gain insight into the central mechanisms of nausea associated with GLP-1R agonists, this study will explore the potential differences at the expected time of C_{max} between a long-acting (albiglutide) and short-acting (exenatide) GLP-1R agonist in brain activation of healthy volunteers, with special interest on regions found in previous research to be associated withvection-induced nausea [[name], 2013, Farmer, 2015]. Nausea central mechanisms are complex. The brain regions associated with pharmacologic orvection-induced nausea have been studied and demonstrated some overlap in the activated regions as well as some divergences [[name], 2013; Miller, 1996].

The drug effects will be studied after a single dose of 50 mg albiglutide and a single dose of 10 μ g exenatide using 1) functional magnetic resonance imaging (fMRI) to assess changes in resting-state blood oxygen level dependent (BOLD) signal, 2) arterial spin labeling (ASL), and 3) magnetic resonance spectroscopy (MRS). The highest approved doses will be used to maximize the potential to observe nausea and the timing of the MRI will overlap with C_{max} . Due to the difference in expected time of C_{max} (albiglutide 3-5 days and exenatide 2 hrs), the timing of MRI and other key study assessments relative to dosing are scheduled to coincide with expected C_{max} timing. Placebo is used to maintain the single-blind.

Observing the rotation of vertical stripes in a rotating drum to create the illusion of self motion (vection) is a well characterized stimulus (task) that can serve as a map of the central response to nausea [[name], 2013; Farmer, 2015]. Each subject will be studied under this standardized condition without the study medication to identify the brain circuitry associated with motion sickness induced nausea (an established vection task). Group analyses will then compare brain outcomes (e.g. connectivity) for motion sickness induced nausea versus nausea induced by different drugs to allow the inference of GLP 1R agonist effects in nausea related brain activation. The group activation maps generated from the vection task scans will also be used to define ROIs to better interrogate the drug-induced alterations in other neuroimaging outcomes (i.e. ASL, MRS). Each subject will act as their own control in this crossover design. The resting-state BOLD and cerebral blood flow (rCBF-ASL) will both be used to provide insight into the connectivity of the central nausea response.

By examining BOLD signals at rest and during task, ASL-rCBF changes and assessing in vivo metabolic changes through MRS [glutamate and gamma-aminobutyric acid (GABA) concentrations], the relationship between neurotransmitter concentration and brain activation/deactivation in specific brain regions will be explored.

The information from this study is expected to be of benefit for patients in the future, as insights on the mechanisms of nausea associated with GLP 1 receptor agonists are needed to design new strategies to minimize the occurrence and impact of these AEs with drugs currently in use, and to design new drugs able to avoid these mechanisms.

